4. PLANNED ANALYSES

The following analysis will be performed for this study: Final analysis including EU/US sites analysis, Japan sites analysis, and pooled analysis of EU/US/Japan sites.

No interim analysis is planned.

4.1. DATA AND SAFETY MONITORING BOARD (DSMB)

An independent DSMB will monitor the study safety data approximately when 33%, 66%, and 100% of the data accrue. DSMB SAP and charter, describing the methodology and presentation of results and access to results are prepared as separate documents.

4.2. INTERIM ANALYSIS

Other than the DSMB safety reviews, there is no interim analysis of the US and EU subjects planned for this study.

Japan cohort enrollment ended earlier than anticipated, and there will only be one database lock for all 3 cohorts. All Type I error will be used for the primary US and EU subjects only analysis.

Document:

Author:

Version Number:

V2.0

Version Date:

21MAY2020

Template No: CS_TP_BS016 Revision 4
Effective Date: 01Apr2016

Reference: CS_WI_BS005

4.3. FINAL ANALYSIS

After the data base lock, all final planned analyses identified in this SAP will be performed by IQVIA Biostatistics following Sunovion authorization of this SAP, Sunovion authorization of analysis populations, and unblinding of treatment.

All population PK/PD analysis will be described in a separate document.

Some minor modifications may be necessary to the planned design of tables, figures, and listings to accommodate data collected during the actual study conduct.

4.4. COHORTS ANALYSIS

In general, all analyses of the Japanese cohort are descriptive in nature. The Japanese cohort will be reported both separately and pooled with the EU and US cohort.

5. ANALYSIS POPULATIONS

Agreement and authorization of subjects included/ excluded from each analysis population will be conducted prior to the unblinding of the study.

5.1. INTENTION-TO-TREAT [ITT] POPULATION

The intention-to-treat (ITT) population will consist of subjects who are randomized, received at least one dose of study medication, and have a baseline and at least one post-baseline efficacy measurement in MADRS Total Score or CGI-BP-S Depression Score. Subjects are included in the ITT population regardless of any protocol deviations. Subjects will be analyzed according to their randomized treatment group.

The ITT population is the primary population for all efficacy analyses.

5.2. PER PROTOCOL [PP] POPULATION

The per protocol (PP) population will consist of all ITT subjects who have no important protocol deviations (IPD), as determined during the IPD review meetings, that may affect the interpretation of the primary efficacy endpoint as defined in [Section 2.6.1](#). See [APPENDIX 7](#) for specifications of IPD. New IPD categories may be created through the review of investigator comments and/or protocol deviations log. The predefined and any new IPDs are defined during the Blinded Data Review (BDR) Process. See [APPENDIX 6](#) for specifications of the BDR Process. Subjects in the PP population will be analyzed according to their randomized treatment group.

Analysis of the primary and the secondary efficacy endpoints will also be performed using the PP population and analyzed according to the randomized treatment group.

Document:

Author:

Version Number:
Version Date:

V2.0

21MAY2020

Template No: CS_TP_BS016 Revision 4
Effective Date: 01Apr2016

Reference: CS_WI_BS005

5.3. SAFETY [SAF] POPULATION

The safety (SAF) population will consist of all subjects who were randomized and received at least one dose of study drug. Subjects will be analyzed according to the predominant treatment received. The predominant treatment is defined as the treatment to which the subject is exposed for the greatest duration during the treatment period. In case of same duration for several treatments, the treatment corresponding to randomization will be considered as predominant.

Duration of exposure to a treatment is calculated as the number of days from first dose date to the last dose date of that treatment. The predominant treatment will generally be the same as the randomized treatment group, unless the subject takes incorrect study drug during their entire participation in the study.

If there is any doubt whether a subject was treated or not, they will be assumed to have been treated for the purposes of analysis.

5.4. PHARMACOKINETICS (PK) POPULATION

The PK population includes the SAF population subjects who have at least 1 valid postdose PK concentration value (including non-missing concentrations < LLOQ) without protocol deviations or events with the potential to affect PK.

The PK analysis will be based on the PK population.

6. GENERAL CONSIDERATIONS

6.1. REFERENCE START DATE AND STUDY DAY

Study Day will be calculated from the reference start date, and will be used to show start/ stop day of assessments and events.

Reference start date is defined as the day of the first dose of study drug, (Day 1 is the day of the first dose of study drug), and will appear in every listing where an assessment date or event date appears.

- If the date of the event is on or after the reference date then:

Study Day = (date of event – reference date) + 1.

- If the date of the event is prior to the reference date then:

Study Day = (date of event – reference date).

In the situation where the event date is partial or missing, Study Day, and any corresponding durations will appear partial or missing in the listings. Partial dates will be presented as is in the listings.

Document:

Author:

Version Number:
Version Date:

V2.0

21MAY2020

Template No: CS_TP_BS016 Revision 4
Effective Date: 01Apr2016

Reference: CS_WI_BS005

6.2. BASELINE

Unless otherwise specified, baseline is defined as the last non-missing measurement taken prior to the reference start date (including unscheduled assessments). In case of subjects randomized but not treated, baseline is defined as the last non-missing measurement taken prior to randomization date. In the case where time isn't available and the date of the last non-missing measurement and the reference start date coincide, that measurement will be considered pre-baseline. Adverse Events and medications commencing on the reference start date will be considered postbaseline.

6.3. DERIVED TIME POINTS

As per protocol, Visit 6 can be an End of Treatment (EOT) visit or an Early Termination (ET) visit. If a subject terminates early, his/her ET visit will be mapped to the next planned assessment visit if it is within the window of the next planned assessment visit. This applies to both efficacy and safety data. If assessments from an ET visit cannot be mapped to the next planned assessment visit, these assessments will be excluded from any mixed model for repeated measures (MMRM) or analysis of covariance (ANCOVA) analysis. No follow-up visit data will be included in any MMRM/ANCOVA analyses. In the case of the ET being out of window of the next planned visit, it will be mapped to an unscheduled visit as appropriate.

All applicable by-visit efficacy and safety tables will include descriptive statistics for the Follow-up visit and the "Last observation visit". The "Last observation visit" is defined as the post-baseline visit at which the last non-missing observation is collected for a subject for a given parameter, including unscheduled visits or unmapped ET visits. The "Last observation visit" will be excluded from any MMRM/ANCOVA analyses.

For remapping of the ET visits, see Table 1 below.

Table 1: Mapping of the ET visit.

Parameter	Early Termination Day Criteria	Week	Analysis Visit
ECG, Vital Sign, YMRS, C-SSRS, Concomitant Medication, Last dose of Benzodiazepines/ Sedatives/Hypnotics	1 ≤ study day ≤ 9	1	Visit 3/Week 1
	10 ≤ study day ≤ 16	2	Visit 4/ Week 2
	17 ≤ study day ≤ 30	4	Visit 5/Week 4
	31 ≤ study day ≤ 44	6	Visit 6/Week 6
MADRS, CGI-BP-S, HAM-A, QIDS-SR16, AIMS, BARS, SAS	1 ≤ study day ≤ 9	1	Visit 3/Week 1
	10 ≤ study day ≤ 16	2	Visit 4/Week 2
	17 ≤ study day ≤ 30	4	Visit 5/Week 4
	31 ≤ study day ≤ 44	6	Visit 6/Week 6
SDS, EQ-5D-5L, Weight, BMI, Waist Circumference, PWC, HbA1C, Lipid panel, Serum Insulin, HOMA-IR, CRP	1 ≤ study day ≤ 44	6	Visit 6/Week 6

Document:

Author:

Version Number:

V2.0

Version Date:

21MAY2020

Template No: CS_TP_BS016 Revision 4
 Effective Date: 01Apr2016

Reference: CS_WI_BS005

Hematology, Serum Chemistry*, Urinalysis, Serum Prolactin, PK, Plasma Prolactin	1 ≤ study day ≤ 16	2	Visit 4/Week 2
	17 ≤ study day ≤ 44	6	Visit 6/Week 6

* Except for parameters listed above such as HbA1C, Lipid panel, Serum Insulin, HOMA-IR, CRP.

Abbreviations: AIMS = Abnormal Involuntary Movement Scale; BARS = Barnes Akathisia Rating Scale; BMI = Body Mass Index; CGI-BP-S = Clinical Global Impression Bipolar Version, Severity of Illness; C-SSRS = Columbia-Suicide Severity Rating Scale; ECG = 12-Lead Electrocardiogram; ET = Early Termination; EQ-5D = EuroQoL-5D; HAM-A = Hamilton Rating Scale for Anxiety; MADRS = Montgomery-Asberg Depression Rating Scale; PWC = Physician's Withdrawal Checklist; QIDS-SR16 = Quick Inventory of Depressive Symptomatology – Self-Report; SAS = Modified Simpson-Angus Scale; SDS = Sheehan Disability Scale; YMRS = Young Mania Rating Scale.

All planned visits will be mapped to weeks and analysis visits for summaries and statistical analyses where applicable (Table 2).

Table 2: Mapping of planned visits.

Planned Visit	Analysis Week	Analysis Visit
Visit 1	-1	Visit 1/Screening
Visit 2	0	Visit 2/Baseline
Visit 3	1	Visit 3/Week 1
Visit 4	2	Visit 4/Week 2
Visit 5	4	Visit 5/Week 4
Telephone Contact (TC)	5	TC
Visit 6	6	Visit 6/Week 6
Visit 7	7	Visit 7/Follow-up/Week 7

Original visit collected on the case report forms (CRFs) will be displayed in the listings.

6.4. RETESTS, UNSCHEDULED VISITS AND EARLY TERMINATION DATA

In general, for by-visit summaries, data recorded at the scheduled visits will be presented.

Unscheduled measurements will not be included in by-visit summaries. Unscheduled measurements collected prior to the first dose of study drug will contribute to the derivation of the baseline value. Unscheduled measurements collected postbaseline will contribute to the derivation of markedly abnormal postbaseline value, and best/worst case value where required (eg, shift tables).

Early termination data collected postbaseline will be assigned to the next planned visit for that assessment as explained in [Section 6.3](#). This mapping will be implemented to all early termination data points used in the efficacy and safety analyses.

Listings will include scheduled, unscheduled (including retests), and early termination data with original dates and visits displayed.

Document:

Author:

Version Number:

V2.0

Version Date:

21MAY2020

Template No: CS_TP_BS016 Revision 4
 Effective Date: 01Apr2016

Reference: CS_WI_BS005

6.5. WINDOWING CONVENTIONS

Apart from early termination data (see [Section 6.3](#)), no visit windowing will be performed during the analysis for this study. Data will be summarized by analysis visit and analyzed by week where applicable (see [Section 6.3](#)).

6.6. STATISTICAL TESTS

All statistical inference will be performed with 2-sided tests at the significance level of 0.05 and 2-sided 95% confidence intervals (CIs), unless otherwise specified in the description of the analyses.

6.7. COMMON CALCULATIONS

For quantitative measurements, change from baseline will be calculated as:

- Test Value at Visit X – Baseline Value

6.8. SOFTWARE VERSION

Apart for the supplementary analysis of the primary endpoint exploring the dose response relationship (generalized MCP-Mod using the DoseFinding package, version 0.9-16) which will use R software version 3.5.3 or higher (R Foundation for Statistical Computing, Vienna, Austria), all other analyses will be conducted using Statistical Analysis System (SAS[®]) version 9.4 or higher (SAS Institute, Inc., Cary, North Carolina).

7. STATISTICAL CONSIDERATIONS

7.1. ADJUSTMENTS FOR COVARIATES AND FACTORS TO BE INCLUDED IN ANALYSES

The following covariates are used in the analyses. For details of their inclusion in the models, see specific analysis sections.

- Baseline value of the variable to be analyzed

7.2. MULTICENTER STUDIES

This study will be conducted by multiple investigators at multiple centers in the US, Europe, and Japan.

When specified, statistical analysis will be adjusted for region with centers within the region pooled.

Document:

Author:

Version Number:
Version Date:

V2.0

21MAY2020

Template No: CS_TP_BS016 Revision 4
Effective Date: 01Apr2016

Reference: CS_WI_BS005

Region will be categorized as follows:

- US
- Europe
- Japan

7.3. MISSING DATA

For the MMRM models, missing observations are treated as missing at random (MAR) and no imputation for missing data will be applied.

Unless otherwise specified, any individual missing item in any scale will not be imputed. When calculating a total score, subscale score, or any assessment with more than one item, if one or more items are missing at a visit, then the associated score (ie, total score or subscale score) will be set to missing. For additional details, see the individual scale description sections.

Handling of missing efficacy data, if any, is described in Sections [16.1.2](#), [16.2.2](#), [16.3.2](#).

Handling of missing safety data, if any, is described in Sections [17.1.1.1](#), [17.1.1.2](#), and [17.6](#).

Handling of missing PK data if any is described in [Section 18](#).

See [APPENDIX 2](#) for details of incomplete/missing dates.

7.4. MULTIPLE COMPARISONS/ MULTIPLICITY

The truncated Hochberg gatekeeping (with the truncation parameter $\gamma = 0.9$) procedure constructed using the general mixture method will be used to control the global Family-Wise Error Rate (FWER) at 5% for the primary (E1) and secondary endpoint (E2) ([Dmitrenko 2016](#)). Using this method, a hypothesis is testable in a latter family only if the hypothesis in the former family associated with the same dose level is rejected.

The hypotheses associated with the primary and the secondary endpoints will be grouped into 2 hierarchical families as seen in Figure 2 below (See [Sections 16.1.3](#) and [16.2.3](#) for the primary hypotheses [H1, H2] and secondary hypotheses [H3, H4]).

- Family F1: SEP-4199 200 mg/day versus placebo (H_1), and SEP-4199 400 mg/day versus placebo (H_2), based on change from baseline in MADRS total score at Week 6 (E1)
- Family F2: SEP-4199 200 mg/day versus placebo (H_3), and SEP-4199 400 mg/day versus placebo (H_4) based on change from baseline in CGI-BP-S depression score at Week 6 (E2)

Document:

Author:

Version Number:

V2.0

[figure not shown]
Version Date:

21MAY2020

Template No: CS_TP_BS016 Revision 4
Effective Date: 01Apr2016

Reference: CS_WI_BS005

Figure 2: Hierarchy of Testing for Primary and Secondary Endpoints

The mixture-based gatekeeping procedure will be performed in 2 steps:

- Step 1: The SEP-4199 vs placebo comparisons for E1 (hypotheses H1 and H2) will be performed using a truncated Hochberg ($\gamma = 0.9$) test.
- Step 2: The SEP-4199 vs placebo comparisons for E2 (hypotheses H3 and H4) will be performed using a regular Hochberg test only when the corresponding comparisons from Step 1 are rejected. For example, H4 is tested only if H2 is rejected.

The primary efficacy analysis will be repeated for the PP population to provide additional information on the robustness of the primary efficacy results. The Hochberg procedure will not be used for the PP population or for the analysis of Japan and pooled cohorts EU/US + Japan.

Adjusted p-values will be calculated using the SAS-based TreeGate macro and available in following website: http://multxpert.com/wiki/TreeGate_macro.

7.5. EXAMINATION OF SUBGROUPS

Subgroup analyses will be conducted as stated in the exploratory analysis sections. It should be noted that the study was not designed to detect treatment differences with high statistical power within subgroups.

The following subgroups will be assessed and described within the appropriate analysis sections:

- Region:
 - US
 - Europe
 - Japan
- Country
- Gender:

Document:

Author:

Version Number:
Version Date:

V2.0

21MAY2020

Template No: CS_TP_BS016 Revision 4
Effective Date: 01Apr2016

Reference: CS_WI_BS005

- Female
 - Male
- Age (years):
 - < 55
 - ≥ 55
- Race in 2 categories:
 - Category 1 for efficacy modeling: White and Non-white (Black or African American, American Indian or Alaska Native, Asian, Native Hawaiian or Other Pacific Islanders, and Other including multiracials)
 - Category 2 for summary statistics for efficacy and safety: White, Non-white, Black or African American, American Indian or Alaska Native, Asian, Native Hawaiian or Other Pacific Islander, and Other including multiracials
- Ethnicity
 - Hispanic or Latino
 - Not Hispanic or Latino
- Bipolar I diagnosis subtype
 - Rapid cycling (4-7 episodes of mood disturbance within the past 12 months)
 - Non-Rapid cycling

8. OUTPUT PRESENTATIONS

[APPENDIX 1](#) shows conventions for presentation of data in outputs.

The templates provided with this SAP describe the presentations for this study and therefore the format and content of the summary tables, figures and listings to be provided by IQVIA.

All tables except efficacy and PK tables will present an overall All SEP-4199 column.

9. DISPOSITION AND WITHDRAWALS

All subjects who provide informed consent will be accounted for in this study.

Subject disposition will be presented for the screened subjects described by the randomized treatment group (where applicable) and overall for all subjects. The number and percentage of subjects who were screened, screen-failed, enrolled, randomized, randomized but not dosed, received study drug, completed or discontinued from the study treatment period, completed the treatment period and the follow-up visit, and completed the treatment period but not the follow-up visit will be presented. The number of subjects with non-missing change from baseline at Week 6 of MADRS total score and CGI-BP-S depression score will also be described. The number of subjects discontinued due to COVID-19 will be summarized and related reasons for discontinuations will be presented by relationship to COVID-

Document:

Author:

Version Number:

V2.0

Version Date:

21MAY2020

Template No: CS_TP_BS016 Revision 4
Effective Date: 01Apr2016

Reference: CS_WI_BS005

19.

With respect to the above, the following definitions apply:

- Screened Subjects: Any subject who signed the study specific informed consent and completed at least 1 study-related procedure.
- Enrolled Subjects: Any subject who was successfully screened and enrolled into the prerandomization period of the study.
- Randomized Subjects: Any subject who was randomized into the treatment period of the study and was assigned a randomization number.

COVID-19 related discontinuations are to be collected on the Disposition CRF page using the disposition reason = "Other" or "Adverse Event". For disposition reason = "Other", the sites are instructed to add the text "COVID-19" in the disposition reason detail. For disposition reason = "Adverse Event" due to COVID-19, the adverse event preferred term will be identified through a predefined MedDRA preferred term search as detailed in [Section 17.1](#).

The number of subjects randomized will also be described by site, country, and region by treatment group and overall. The number of subjects who complete (including remotely versus in-person, for Week 6 and the Follow-up visit only) and discontinue from the study drug before or at a given visit, along with reasons for study drug discontinuation, including due to COVID-19, will be described by the treatment group and overall using randomized subjects. Time to discontinuation from study drug will be plotted using a Kaplan-Meier (KM) curve.

The number of subjects in each population will also be described.

10. PROTOCOL DEVIATIONS

Important protocol deviations (IPDs) will be identified and documented based on blinded reviews of data listings. The IPD categories may include, but may not be limited to:

- Eligibility and Entry Criteria
- IP Compliance
- Concomitant Medication Criteria
- Laboratory Assessment Criteria

Further details on the identification of IPDs are provided in [APPENDIX 7](#).

IPDs will be identified for all randomized subjects and presented in data listings. The number and percentage of subjects within each IPD category will be summarized by treatment group and overall for the ITT population.

In addition, the number and percentage of subjects with major and critical protocol deviations that were not considered to be IPDs will be also summarized by treatment group and overall for the ITT population.

Document:

Author:

Version Number:

V2.0

Version Date:

21MAY2020

Template No: CS_TP_BS016 Revision 4
Effective Date: 01Apr2016

Reference: CS_WI_BS005

In general, major and critical protocol deviations are defined as follows:

- Major: A deviation from protocol-related procedures that could affect the integrity of the data or adversely affect subjects.
- Critical: A deviation from protocol-related procedures that threatens integrity of the data, adversely affects subjects and/or could invalidate acceptability of a project (or part of it).

10.1. DEVIATIONS RELATED TO PK ANALYSIS

Changes to the procedures or events, which may impact the quality of the PK data, may be considered significant protocol deviations and will be described within the clinical study report body text. These changes or events will include any circumstances that will alter the evaluation of the PK. Examples include, but may not be limited to, vomiting following oral dosing occurring within the time frame of 2 times the median t_{max} , sample processing errors that lead to inaccurate bioanalytical results, and/or inaccurate dosing on the day of PK sampling. In the case of a significant protocol deviation or event, PK data collected for the affected dose group will be excluded from the study summary and inferential results but listed, if appropriate. Other changes to the procedures or events which do not impact the quality of the PK data will not be considered significant. A common example of a non-significant protocol deviation is a missed blood sample or deviations from blood collection times.

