15.2. Analysis Populations

Each population below will be created for both the US and Europe cohort and the Japanese cohort.

Intention-to-Treat Population: The intention-to-treat (ITT) population will consist of subjects who are randomized. Subjects are included in the ITT population regardless of any protocol deviations. Subjects will be analyzed according to their randomized treatment group. The ITT population is the primary population for all efficacy analyses.

Per Protocol Population: These are all ITT subjects who have no important protocol deviations that may affect the interpretation of the primary efficacy endpoint as defined in [Section 15.3.3](#). Subjects in the Per Protocol population will be analyzed according to their randomized treatment group.

Analysis of the primary and the secondary efficacy endpoints will also be performed using the Per Protocol population.

Safety Population: The safety population will consist of all subjects who randomized and receive at least one dose of study medication. Subjects will be analyzed according to the predominant treatment received. The predominant treatment is defined as the treatment to which the subject is exposed for the greatest duration during the treatment period. This will generally be the same as the randomized treatment group, unless the subject takes incorrect study medication during their entire participation in the study.

Pharmacokinetic (PK) Population: The PK population includes the Safety population subjects who have at least 1 valid postdose PK concentration value without protocol deviations or events with the potential to affect PK. The PK analysis will be based on the PK population.

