18. PHARMACOKINETIC ANALYSIS

All PK analysis will be performed using PK population.

Blood sample for plasma concentrations of R-amisulpride, S-amisulpride, total amisulpride, and/or plasma prolactin measurement will be collected at Visit 1/Screening (only for plasma prolactin), Visit 2/Baseline/Day -1, Visit 4/Week 2, Visit 6/Week 6, and Visit 7/Follow-up/Week 7. The PK collection times from Predose on Day -1 to Follow-up and deviations and/or any values excluded from analysis will be presented in data listings. Any plasma concentration or summary statistics below the lower limit of Document:

Author:

Version Number:
Version Date:

V2.0

21MAY2020

Template No: CS_TP_BS016 Revision 4
Effective Date: 01Apr2016

Reference: CS_WI_BS005

quantification (LLOQ) will be represented by "BLQ" (below the limit of quantification) in tables and listings. Amisulpride plasma concentration will not be presented for the placebo group.

R-amisulpride, S-amisulpride, total amisulpride, and plasma prolactin concentrations at each scheduled sample collection time point (including ET and Follow-up, see [Section 6.3](#) for mapping of the ET visit) will be summarized descriptively (n, mean, median, minimum, maximum, coefficient of variation [CV] and if appropriate, geometric mean and geometric CV [GCV]). In addition, if there is at least 1 concentration < LLOQ within a treatment group at a time point, it will be set to $\frac{1}{2}$ LLOQ for summary statistics calculations. A second approach will be to assume a truncated normal distribution for the specific concentration data if at least 10% of the concentrations at a time point are < LLOQ within a treatment group. The mean and variance of truncated normal will be calculated ([APPENDIX 3](#)). Number and percentage of concentrations that are below the LLOQ will be provided for each visit. All PK summaries will be presented by dose.

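### SAP 10.1 excludes PK data by dose group, while the rest of the plan excludes by subject or by value

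*SAP*

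**What the plan says.** **SAP 10.1 (Deviations Related to PK Analysis).** Changes or events that may impair the PK data "may be considered significant protocol deviations and will be described within the clinical study report body text". The examples are vomiting within twice the median time to peak, and "sample processing errors that lead to inaccurate bioanalytical results, and/or inaccurate dosing on the day of PK sampling". The trigger is worded in the singular ("In the case of a significant protocol deviation or event"), and the consequence attached to it is that "PK data collected for the affected dose group will be excluded from the study summary and inferential results but listed, if appropriate". The section sets no minimum number of events and does not limit the exclusion to a subject, a sample or a visit.

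**SAP 5.4 and protocol 15.2 (PK population).** SAP 5.4 takes safety-population subjects with at least one valid postdose concentration "without protocol deviations or events with the potential to affect PK". The protocol's definition has the same form: "The PK population includes the Safety population subjects who have at least 1 valid postdose PK concentration value without protocol deviations or events" that could affect PK.

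**SAP 18 (Pharmacokinetic Analysis).** All PK analysis uses the PK population, and "deviations and/or any values excluded from analysis will be presented in data listings". Protocol 15.3.7 makes the same provision for listing excluded values. On layout, "All PK summaries will be presented by dose", and amisulpride concentrations are not shown for placebo.

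**The concern.** The trigger in SAP 10.1 is a single event, and its examples happen to one person or one tube. The stated consequence falls on everyone assigned to the same dose. The other four sections that bear on PK exclusions work at a finer level. An analyst who follows SAP 10.1 to the letter and one who follows SAP 18 would produce different tables from the same data.

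At stake is the SAP's descriptive summary of R-, S- and total amisulpride by dose and visit, together with the active-arm columns of the plasma prolactin summary. With two active doses and placebo not shown for amisulpride, losing one dose group leaves one column.

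**Working it through.** **1. The units side by side.** Take one spoiled sample, at Visit 4, in one subject.

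| Section | Unit of exclusion | What is removed |
|---|---|---|
| SAP 10.1 | Dose group | All PK data from every subject on that dose |
| SAP 5.4, protocol 15.2 | Subject | All of that subject's values; or, if one clean postdose value is enough to qualify, the subject stays |
| SAP 18, protocol 15.3.7 | Value | That one concentration |

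The general rules for important deviations do not settle this. Neither SAP 10 nor SAP Appendix 7 has a category for PK deviations.

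**2. Planned group size.** SAP 3.4 gives 93 evaluable subjects per group, an upward adjustment of about 5%, and 98 randomized per group. 93 / 0.95 = 97.9 and 93 × 1.05 = 97.65; both round up to 98, so the figure reproduces. SAP 3.1 gives 15 per group for Japan.

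**3. Active subjects (two active groups).**
- US and Europe: 2 × 98 = 196
- Japan: 2 × 15 = 30
- Pooled, as SAP 4.4 also provides: 98 + 15 = 113 per group, and 2 × 113 = 226

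**4. Loss from one event under SAP 10.1 read literally** (group size / active subjects).
- US and Europe: 98 / 196 = 50%
- Japan: 15 / 30 = 50%
- Pooled: 113 / 226 = 50%

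**5. Loss from the same event under subject-level exclusion.**
- US and Europe: 1 / 98 = 1.0% of the dose column, 1 / 196 = 0.5% of active subjects
- Japan: 1 / 15 = 6.7% and 1 / 30 = 3.3%
- Pooled: 1 / 113 = 0.9% and 1 / 226 = 0.4%

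Under value-level exclusion the loss is one value at one visit, and the subject's other visits are untouched.

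**6. How likely a trigger is.** The documents give no rate for significant PK deviations. As illustration only, assume independent subjects and a rate p per subject between 0.1% and 5%. The chance that at least one of the two US/Europe active groups has an event is 1 − (1 − p)^196: 17.8% at 0.1%, 86% at 1%, and about 100% at 5%. The conclusion does not rest on these figures.

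**The case against.** The strongest reply is that nobody would apply SAP 10.1 this way. SAP 18 governs the PK analysis, uses a population defined by subject, and speaks of individual excluded values. A programmer working from it would not blank a dose column, and the reference to the dose group is probably loose wording. Classifying an event as significant is also a matter of judgement, and the vomiting example depends on a median time to peak that the SAP's PK section does not derive.

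Most of this stands, and it is why the point is a conflict between sections rather than a forecast of lost data. It does not remove the defect. The judgement covers only whether an event counts as significant; the exclusion that follows is mandatory. The closing qualifier in that sentence attaches most naturally to the listing and does not narrow the exclusion to a subject. If SAP 10.1 is to be disregarded, the plan does not say so, and the choice between subject and value is left open.

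A reader might infer that the trial stands to lose half of its PK data, or could not meet its PK objectives for both doses. The documents do not support that. The rule concerns summary and inferential results, and the data may still be listed. SAP 18 specifies no PK hypothesis test. Population PK/PD, which serves the population PK objective, is described in a separate document (SAP 4.3) and reported separately from the study report (SAP 3.7), and nothing shows that SAP 10.1 governs that dataset.

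**Conclusion.** SAP 10.1 conflicts with SAP 5.4, SAP 18, protocol 15.2 and protocol 15.3.7 on the unit of PK exclusion, and its own wording is wrong as written. If it is applied literally, one event costs one of the two active columns in the descriptive amisulpride summary, which is 50% of planned active subjects in either cohort. Under subject-level exclusion the cost is about 1% of a column in the US and Europe and 6.7% in Japan.

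The 50% is conditional on the literal reading. The counts are planned randomized subjects; the PK population will be smaller, but with 1:1 allocation one dose group should remain close to half. Efficacy results are unaffected. This is a minor point, worth correcting because the correction is simple and has no drawback.

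**What to change.** Before unblinding:

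- In SAP 10.1, replace the reference to the dose group's PK data with the affected PK concentration value(s) of the subject concerned. This matches the value-level provision in SAP 18 and protocol 15.3.7.
- In SAP 5.4, state that a subject stays in the PK population if at least one valid, unaffected postdose value remains. Without this, SAP 10.1 would work by value while SAP 5.4 could still be read as dropping the whole subject.

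The cost is one phrase in SAP 10.1 and one clarifying clause in SAP 5.4. Data collection, sample size and the efficacy analyses do not change.
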